EFFECTS OF THE GLP-1 RECEPTOR AGONIST LIRAGLUTIDE ON LOWER LIMB PERfusion IN PEOPLE WITH TYPE 2 DIABETES AND PERIPHERAL ARTERY DISEASE: A RANDOMIZED CONTROLLED TRIAL (STARDUST)

ClinicalTrials.gov identification number: NCT04881110

Study Protocol (version 2_0401_2021)

Principal investigator: [name]

Full professor of Endocrinology and Metabolic Diseases, University of Campania Luigi Vanvitelli

Chief of the Division of Endocrinology and Metabolic Diseases, University Hospital of Campania Luigi Vanvitelli

Introduction

Diabetes represents a severe social and health burden. Among chronic complications of diabetes, peripheral artery disease (PAD) is involved in diabetic foot ulcer onset and prognosis. PAD diagnosis is based on several assessments: ankle-brachial index (ABI) is a common and simple evaluation. However, it can often be unreliable because of arterial calcification, which is frequent in people with diabetes. Transcutaneous oxygen tension (TcPO₂) evaluation is a non-invasive approach to measure tissue's perfusion and oxygenation. Moreover, it is currently recommended to detect the grade of peripheral ischemia in individuals with diabetic foot ulcers. Furthermore, low values of TcPO₂ have been associated with the high risk of lower limb amputation, reduction of the healing rate and major cardiovascular events.

Optimal glycemic control has been related to the reduction of the incidence of chronic complications of diabetes. Moreover, among novel glucose-lowering therapies, GLP-1 receptor agonists (GLP-1RAs) have proven over time cardiovascular benefits in cardiovascular outcome trials. Indeed, GLP-1 receptors are widely expressed in endothelial and cardiovascular cells; this may contribute to improve endothelial function and angiogenesis, prevent endothelial cells apoptosis and reduce oxidative stress and inflammation.

GLP-1RAs have determined a significant reduction of major cardiovascular events in cardiovascular outcome trials in people with type 2 diabetes. Moreover, a post-hoc analysis of LEADER trial has described the safety of liraglutide (vs. placebo) in terms of risk of diabetic foot ulcers and/or infection and peripheral revascularization. Of interest, a significant reduction of the incidence of lower extremities amputation occurred in participants of the study with diabetic foot syndrome who were treated with liraglutide.

[figure not shown]
Aims

“Effects of the GLP-1 receptor agonist liraglutide on lower limb perfusion in people with type 2 diabetes and peripheral artery disease: a randomized controlled trial (STARDUST)” is designed to determine the effect of injectable liraglutide on peripheral perfusion in individuals with type 2 diabetes and PAD. Peripheral perfusion will be assessed through the $TcPO_2$ measurement on the foot. Moreover, we will evaluate the effect of GLP-1RAs on parameters of glyco-metabolic control, inflammation, angiogenesis and cardiovascular risk markers. Particularly, we will analyze:

- glyco-metabolic parameters [fasting glucose, glycated hemoglobin (HbA_{1c}), weight, body mass index (BMI), waist circumference, systolic and diastolic blood pressure];
- lipid profile (total cholesterol, LDL cholesterol, HDL cholesterol, triglycerides);
- inflammation markers [C-reactive protein (CRP), fibrinogen, tumor necrosis factor alpha, interleukin-6];
- renal function parameters [creatinine, azotemia, urine albumin to creatinine ratio (UACR), glomerular filtration rate (eGFR)];
- angiogenesis markers [endothelial progenitor cells (EPCs) and vascular endothelial growth factor (VEGF)];
- PAD clinical assessment (ABI, 6-minutes walking test);
- sexual hormones levels and sexual function.

Study design

STARDUST is a single-center, randomized clinical trial lasting 24 weeks. The study will include a screening visit, a randomization visit and 2 follow-up visits (3 month and 6 month).

Study population

Eligibility will be considered for individuals with type 2 diabetes aged > 35 years, PAD diagnosed through doppler ultrasound, angio-CT, angiography in the past 12 months, TcPO₂ value of the foot ranged between 49 and 30 mmHg.

Inclusion criteria

- diagnosis of type 2 diabetes
- HbA_{1c} ranged between 6.5% and 8%
- Glucose-lowering therapy with metformin and/or insulin on stable doses for at least 3 months

Exclusion criteria

- diagnosis of type 1 diabetes
- current or recent treatment with GLP-1RAs and/or DDP-4 inhibitors
- participation to other clinical research, including drug administration
- contraindications to the treatment with GLP-1RAs
- plans for pregnancy or current pregnancy or breast feeding
- history of thyroid disease
- inflammatory bowel disease
- acute coronary and/or cerebravascular disease within the previous 14 days
- plans and/or indications to peripheral revascularization procedure
- estimated glomerular filtration rate (eGFR) below 15 ml/min per 1.73m²
- previous history or current diagnosis of neoplasms and/or anti-neoplastic therapies within 5 years from randomization
- history of diabetic ketoacidosis
- current therapies with steroids and/or anti-psychotic medications
- any concomitant conditions which can preclude participation in the study

Female participants in fertile age have to use contraceptives during the study. Moreover, women who meet inclusion criteria will be screened for pregnancy before the completion of the enrollment.

Randomization

Randomization using a computer generated random-number sequence.

Allocation

Concealed in sealed study folders that will be held in a central, secured location until after informed consent will be obtained.

Interventions

LIRA GROUP: participants assigned to LIRA group will start on 0.6 mg once daily liraglutide subcutaneous injection at approximately the same time of the day. The dose will be titrated up on a weekly schedule by 0.6 mg increase to a target dose of 1.8 mg or the maximum tolerated. In accordance with standards of medical care, cardiovascular risk factors will be managed as follows:

systolic blood pressure below 130 mmHg and diastolic blood pressure below 80 mmHg obtained, if needed, with ACE inhibitors or angiotensin receptor blockers, LDL-cholesterol below 70 mg/dL, aspirin therapy at the dosage of 100 mg daily or alternatively clopidogrel 75 mg daily in case of documented aspirin allergy.

CONTROL GROUP: individuals assigned to control group will be given, if needed, tailored therapeutic prescriptions to manage blood glucose levels and cardiovascular risk factors, according to the standards of medical care. The established treatment goals for cardiovascular risk factors control will be: systolic blood pressure below 130 mmHg and diastolic blood pressure below 80 mmHg obtained, if needed, with ACE inhibitors or angiotensin receptor blockers, LDL-cholesterol below 70 mg/dL, aspirin therapy at the dosage of 100 mg daily or alternatively clopidogrel 75 mg daily in case of documented aspirin allergy.

Recruitment and time schedule

Recruitment will last 18 months. Participants will be followed up for 24 weeks (6 months).

Time schedule	Visit 1 (Screening)	Visit 2 (Randomization)	Visit 3 (3 months follow- up)	Visit 4 (End of the study)
	Week -1	Week 0	Week 12	Week 24
Informed consent	x			
Eligibility evaluation	x			
Pregnancy screening test [†]	x			
Start of the intervention		x		
Anamnesis and clinical assessment	x			
Physical examination: weight, BMI, WC		x	x	x
Blood pressure evaluation		x	x	x
Glycemic profile evaluation: fasting glucose, HbA _{1c}	x	x	x	x
Lipid profile evaluation: total cholesterol, LDL-chol, HDL-chol and triglycerides		x	x	x
Renal function evaluation: creatinine, azotemia, eGFR	x	x	x	x
Inflammation markers: CRP, fibrinogen, TNF- α and IL-6		x		x
Angiogenesis markers: EPCs and VEGF		x		x
Sexual hormones evaluation: testosterone or estradiol, LH, FSH, SHBG*		x		x
Albuminuria		x		x

ABI and 6-minute walking test		x		x
TcPO ₂	x	x	x	x
IIEF-5 questionnaire*		x		x
FSFI questionnaire†				
Adverse events evaluation		x	x	x

*In males; †In females.

ABI, Ankle Brachial Index; BMI, Body Mass Index; CRP, C-reactive protein; EPC, Endothelial Progenitor Cell; eGFR, estimated Glomerular Filtration Rate; FSFI, Female Sexual Function Index; FSH, Follicle-stimulating hormone; IL-6, Interleukin 6; IIEF-5, International Index of Erectile Function 5; LH, Luteinizing hormone; SHBG, Sex hormone-binding globulin; TcPO₂, Transcutaneous Oxygen Pressure; TNF- α , Tumor Necrosis Factor α ; VEGF, Vascular Endothelial Growth Factor; WC, Waist circumference.

Study withdrawal

Subjects may withdraw from the research at any time for:

- voluntary retirement;
- occurrence of adverse event which requires the end of the study;
- poor adherence to trial intervention and/or follow-up;
- modification of inclusion/exclusion criteria from baseline;
- novel treatment with medications interfering with the endpoints evaluation;
- pregnancy.

Investigators may interrupt the research in case of:

- occurrence of adverse events (nausea, vomit, abdominal pain, fever, rush and/or eosinophilia);
- renal function worsening (eGFR <15 mL/min/1.73m²);
- dialysis or renal transplantation;
- chetoacidosis (confirmed by laboratory tests);
- occurrence of acute or chronic pancreatitis;
- medullary carcinoma diagnosis after randomization;
- any adverse event or relevant clinical event, considered as an interference for the research;
- any allergic reactions;
- recruitment of the individual in other study interfering with the research.

Primary outcomes

The co-primary outcomes of the study are the peripheral perfusion assessed at baseline and at the end of the study and the proportion of individuals who reaches a 10% increase of the TcPO₂ value from the baseline in each group. The change of TcPO₂ of the foot in people treated with liraglutide compared with individuals of the Control group will be calculated after 6 months. The TcPO₂ change will be evaluated as the difference between TcPO₂ values measured at the end of the trial and baseline.

Secondary outcomes

The secondary outcomes of the study are the change (measured as the difference of variables at the end of the trial vs. baseline) in glyco-metabolic, inflammation and angiogenesis, atherosclerosis

parameters in people treated with liraglutide compared with individuals of the Control group. Moreover, we will evaluate the changes in renal function, sexual hormones levels and sexual function.

18-month extension of the follow-up

An 18-month extension of the follow-up will be performed for all the study population, according to guidelines and good clinical practice. The follow-up will include the glyco-metabolic parameters and the main cardiovascular risk factors, including TcPO₂ assessment.

Data from this extended observation will be collected for additional analyses (mostly regarding the durability of the effects). Individuals who will be lost during follow-up and/or discontinue or modify the glucose-lowering treatment will be excluded from the analyses.

Methods

All individuals will be informed about the aims of the study through a specific information letter. Moreover, during the screening visit, we will collect written informed consent and deliver an information letter for the general practitioner of each participant.

Physical examination - Height and weight will be recorded using the Seca 200 scale, with attached altimeter (Seca, Hamburg, Germany). The WC will be measured in orthostatic position, at anterior-superior iliac spine, using a graduated instrument. BMI will be calculated as weight in kg divided by the height in squared meters (kg/m²). Blood pressure will be measured three times, with patients in sitting position, after at least 15 minutes of rest.

Laboratory assessments – Blood samples will be collected for the evaluation of glycemia, HbA_{1c}, creatinine, serum lipids, according to the attached time-schedule. Calculation of the glomerular filtration rate will be performed using the MDRD formula. Participants will be tested for levels of testosterone, estradiol, LH, FSH and SHBG according to sex. Serum lipids will be determined by enzyme immunoassay. Albuminuria will be measured on 24-hour urine sample and defined as microalbuminuria for urinary albumin excretion values between 30 and 299 mg/24h and macroalbuminuria for values greater than 300 mg/24h.

Inflammation - Serum samples for cytokines, CRP and VEGF will be stored at -80°C until measurements will be performed. Serum concentrations of IL-6, TNF- α and VEGF will be determined in duplicate using highly sensitive immunoenzymatic kits (Quantikine HS, R&D System, Minneapolis, Minn). High sensitivity CRP will be measured by immunonephelometric method.

Determination of circulating levels of EPCs - Each patient will provide a blood sample to determine EPCs count. Cells derived from peripheral blood will be studied for the evaluation of surface antigen expression by flow cytometry. Mononuclear cells will be isolated from peripheral venous blood by density gradient centrifugation and subsequently incubated for 30 min at 4°C in dark field with monoclonal antibodies conjugated to fluorescein isothiocyanate (FITC) for human CD34+ cells (MAb) (Becton Dickinson, Buccinasco, Bologna, Italy), phycoerythrin (PE) conjugated antibodies for human KDR+ cells (MAB) (R&D Systems, Minneapolis, MN, USA), and allophycocyanin (APC) conjugated antibodies for human CD133+ cells (Miltenyi Biotec, Calderara

di Reno, Bologna, Italy). After incubation, a quantitative analysis will be performed using BD FACSCalibur and 1,000,000 events will be acquired from each sample. The use of a morphological gate will be employed for the exclusion of granulocytes. Subsequently, CD34+ or CD133+ cells will be identified in the mononuclear cell fraction and these populations will be examined for simultaneous expression of KDR. CD34+CD133+ cells will be identified in the two-dimensional analysis of the dot-plots. The KDR+ mononuclear cell pool will be identified separately. Cells with triple positivity for the considered markers will be searched within the group of CD34+ cells, due to the double expression of KDR and CD133. Data will be processed using the Macintosh CELLquest software (Becton Dickinson). The set-up of the instrument will be optimized daily by analyzing the expression of lymphocytes derived from peripheral blood labeled with antiCD4Fitc/CD8, Pe/CD3, Pecy5/CD45 Apc 4-, in combination of 4 colors.

Clinical assessment of atherosclerosis – The ABI of both limbs will be calculated through the ratio between the systolic pressure registered at the posterior tibial artery and the systolic pressure recorded at the brachial artery, after at least 15 minutes of rest and in the supine position. The 6-minute walking test will be performed by each participant, walking up and down in a 100 meters hallway. Individuals will receive instructions to cover as much distance as possible in 6 minutes.

Erectile Function Assessment - Male patients will perform a self-assessment test (IIEF-5) of their erectile function and overall satisfaction with sexual life, referring to the previous 6 months. Erectile dysfunction (ED) will be classified based on the total questionnaire score. Any score ≤ 21 will indicate the presence of ED [mild (score 21-17), mild-moderate (score 16 -12), moderate (score 11-8) and severe (score 7-1)]. The IIEF-5 questionnaire will be administered at visit 2 (week 0) and at the end of the study (week 24).

Assessment of Female Sexual Function – Female sexual function will be studied through the FSFI questionnaire which assesses sexual activity over the past 4 weeks and includes 19 questions. The questionnaire will investigate six distinct domains (sexual desire, arousal, lubrication, orgasm, satisfaction and pain), and provide a total score indicative of global sexual function. A total FSFI score < 26.55 will be used to classify the presence of female sexual dysfunction. The FSFI questionnaire will be administered at visit 2 (week 0) and at the end of the study (week 24).

Evaluation of TcPO₂ - The measurement of transcutaneous oxygen tension will be performed on both limbs of each participant. Anterior tibial artery perfusion will be assessed near the base of the third finger, while posterior tibial artery perfusion will be evaluated near the lateral malleolus. The patients will be examined in supine position, after 20 minutes of rest. The application of the electrodes has to avoid areas with bony prominences, superficial veins or skin lesions. Measurement sites will be cleaned with an alcoholic solution, the electrodes will be fixed to the skin through an adhesive ring, after the application of a contact solution. Before each measurement, the oximeter will be calibrated for at least 10 minutes. The TcPO₂ measurement will be recorded for 16 minutes. According to manufacturer sheet, TcPO₂ value ≥ 50 mmHg is considered as indicator of a normal perfusion, while TcPO₂ value < 30 mmHg is referred to critical ischemia. The lowest value of each participant will be considered for the follow-up and the analysis.

Planned statistical analysis

The sample size calculation was performed based on the change of the primary endpoint (change in $TcPO_2$). Assuming an estimated standard deviation of 5 mmHg, a dropout rate of 10%, we expect to require at least 50 participants (in a 1:1 ratio LIRA:Control strategies) to achieve the 90% power to detect an 10% difference between group at a α -level of 0.05.

Descriptive statistics will be used for demographic and baseline clinical characteristics of all participants in the study. Continuous variables will be described as either mean and standard deviation (SD) or medians and interquartile range (IQR) according to sample distribution, and count data will be reported as numbers and percentages. Comparisons of baseline data between groups will be performed by Student's t test or Mann-Whitney Rank Sum test, depending on the normality of sample distribution. Comparison among frequencies was made with the χ^2 test.

To evaluate the change of variables over time Δ values will be calculated as value at the last observation minus value at the start. The paired t test and Wilcoxon signed rank test within each patients' group will be used to assess changes in the studied variables from baseline to the last observation. Two-sample t-test will be used to compare differences between interventions. The χ^2 test will be used for comparing proportions of participants in the 2 groups who reached the primary endpoint after the intervention. Relative Risk (RR) and 95% confidence interval (CI) will be calculated to demonstrate the relationship between the intervention and the achievement of the primary endpoint. Data were also analyzed by analysis of variance for repeated measures with a post-hoc comparisons made with the Scheffé's test. P value < 0.05 will be considered statistically significant. All analyses will be conducted using SPSS version 19.0 (SPSS Inc, Chicago, Ill).

Safety and Adverse Events

Adverse event (AEs) - Any unexpected event occurred in a patient included in a clinical trial after the administration of a pharmacological product. This event is not necessarily related to pharmacological treatment. Therefore, an AE, may be any unpleasant and unwanted clinical sign (for example, an abnormal laboratory finding), symptom, or disease, which is transiently associated with the use of a drug. According to the guidelines of the Common Terminology Criteria for Adverse Events (<https://www.fda.gov/downloads/Guidances/UCM174090.pdf>), AEs will be divided in different grades.

- Grade 1 (mild): lack of symptoms or mild symptoms, with no indication to specific intervention; clinical or diagnostic observation is required.
- Grade 2 (moderate): moderate symptoms requiring local or non-invasive intervention; it may determine a limitation of daily activities.
- Grade 3 (severe or clinically significant, but not immediately life-threatening): requiring hospitalization. It may determine disability and heavily limit daily activities.
- Grade 4 (life-threatening event): indication to urgent intervention.
- Grade 5: death related to AE.

Adverse drug reaction (ADR) - An ADR is defined as a noxious and unintended response to drug administration. It occurs determining pathological changes with doses which are normally used in

humans for prophylaxis, diagnosis, or therapy of a disease. The relationship between the drug administration and the adverse event is reasonably possible and, in any case, cannot be excluded.

Serious Adverse Event (SAE) – A SAE is defined as any adverse clinical event that is fatal or life-threatening, which requires hospitalization and leads to a significant disability. It also includes congenital anomalies/birth defects, or any serious medical event that investigator would report.

Hospitalization will be considered as SAE if:

- duration of hospitalization lasts more than 12 hours;
- hospitalization was not previously planned;
- hospitalization is not connected to an AE.

Disability is defined as the significant loss of any ability useful for carrying out normal vital functions.

Unexpected Adverse Reaction or Suspected Unexpected Serious Adverse Reaction (SUSAR) – A SUSAR is a severe and unexpected reaction which is also considered unpredictable, according to drug information (for example, medication data sheet).

Overview of Adverse Event Evaluation

- Type, frequency, severity and severity/intensity of all AEs
- Number of patients discontinuing treatment due to the occurrence of any AE
- Clinically significant changes in ECG, vital signs and laboratory tests

If any AE/SAE occurs, investigator will have the responsibility to report the suspected adverse drug reaction to the Service of Pharmacovigilance, in accordance with current legislation. Moreover, serious adverse events must be notified to pharmacovigilance manager within 24 hours of the awareness. Furthermore, SUSARs must be notified to the Authorities and Ethical Committee.

Pregnancy

Pregnancy is an exclusion criteria for the study, since GLP-1RAs have no indications in pregnancy. If pregnancy occurs in patients taking liraglutide:

- 1) treatment with liraglutide will be immediately stopped;
- 2) pharmacovigilance manager will receive notification (within 24 hours);
- 3) women will be monitored until the end of the pregnancy.

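### The withdrawal section lets participants leave the study itself, not just study treatment, for new medication or changed eligibility, so week-24 data could be lost for reasons tied to outcome or to control care

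*Protocol*

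**What the plan says.** The Study withdrawal section of the protocol opens its first list with "Subjects may withdraw from the research at any time for". What is left is the research, and no arm is named. Among the reasons are "modification of inclusion/exclusion criteria from baseline" and "novel treatment with medications interfering with the endpoints evaluation". A participant's own choice to leave is a separate item. A second list gives the grounds on which investigators may interrupt the research. It names neither new medication nor general loss of eligibility.

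The criteria that could change are in the eligibility text. The inclusion bullets contain "HbA_{1c} ranged between 6.5% and 8" (per cent) and a requirement for stable metformin and/or insulin doses over the preceding three months. The exclusion bullets include planned or indicated peripheral revascularisation. The Study population paragraph, outside the bulleted list, adds "TcPO₂ value of the foot ranged between 49 and 30 mmHg".

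Under Interventions, "individuals assigned to control group will be given, if needed, tailored therapeutic prescriptions to manage blood glucose levels and cardiovascular risk factors". Under Primary outcomes, TcPO₂ change is taken from baseline to the end of the trial, and a co-primary outcome is "the proportion of individuals who reaches a 10% increase of the TcPO₂ value from the baseline in each group". Planned statistical analysis computes change from the last observation available. For the 18-month extension only, the protocol adds: "Individuals who will be lost during follow-up and/or discontinue or modify the glucose-lowering treatment will be excluded from the analyses".

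**The concern.** A change in eligibility status or the start of a new drug is an ordinary reason to review study treatment. It is not in itself a reason to stop measuring the participant. The section draws no such line, and nothing in the 24-week text says that a participant who leaves for these reasons still attends the remaining visits.

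The two reasons are not neutral. A drug that interferes with the endpoints is likely to be started because the condition under study has changed. Several eligibility criteria are outcomes, or move with disease or with care. No placebo or blinding is described, so whether someone leaves could depend on the arm. If the reasons are used, those who remain at week 24 are a selected group, possibly selected differently in each arm.

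How to handle missing values can be left to a statistical analysis plan. Whether the values are collected at all is settled by the protocol.

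**Working it through.** **The plan's own sample size.** Inputs from Planned statistical analysis: SD 5 mmHg, 90% power, α 0.05 (taken as two-sided), 10% dropout, 50 participants at 1:1. The 10% difference has no stated base in mmHg. With the normal approximation, n per arm = 2 × (1.960 + 1.282)² × 5² / δ².
- δ = 5.0 (10% of 50): 21.0, rounded up to 22.
- δ = 4.9 (10% of 49): 21.9, rounded up to 22.
- Dropout: 22 / 0.9 = 24.4, so 25 per arm and 50 in total. The stated figure is reproduced on these bases.
- Allowance: 25 × 0.10 = 2.5 losses per arm. Each participant is 1/25 = 4% of an arm.

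**Which changes could count as a listed reason.**
- HbA1c of 6.5% to 8% is a bulleted criterion, a studied outcome and the target of a glucose-lowering drug given to one arm. It is remeasured at weeks 12 and 24 and can leave the range at either end.
- Stable metformin or insulin doses: a control whose insulin is adjusted under the tailored prescriptions no longer meets this, through assigned care.
- No indication for revascularisation: a participant whose limb worsens enough to need the procedure no longer meets this.
- New medication: a control given a new glucose-lowering drug can be read as meeting this reason, because fasting glucose and HbA1c are endpoints.
- TcPO₂ of 30 to 49 mmHg counts only if the Study population sentence is taken as part of the inclusion criteria.

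**What an early leaver would lack.** Six rows of the schedule are marked only at weeks 0 and 24: inflammation, angiogenesis, sexual hormones, albuminuria, ABI with the walking test, and IIEF-5. The Methods text gives the same timing for FSFI. None would have a post-baseline value. TcPO₂ would have a week-12 value at best. The last-observation rule could use it, but the primary outcome is defined at the end of the trial.

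**TcPO₂ on the broad reading.**
- A 10% rise passes 49 when baseline exceeds 49 / 1.1 = 44.5. In whole numbers that is 45 to 49 (45 gives 49.5, 49 gives 53.9), or 5 of the 20 values from 30 to 49.
- A 10% fall goes below 30 when baseline is under 30 / 0.9 = 33.3. In whole numbers that is 30 to 33 (33 gives 29.7), or 4 of 20.

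**Illustration of scale only.** None of these assumptions is in the protocol, apart from the SD of 5 mmHg, applied here to change at both visits.
- Upper-end case: baseline uniform on 30 to 49, 70% of the effect present at week 12, correlation of changes 0.5 or 0.7, and everyone outside 30 to 49 at week 12 leaves. With a true effect of 5 mmHg, about 26% of the liraglutide arm and 21% of controls go, and the completer difference is 4.36 to 4.54. With a true effect of 4 it is 3.48 to 3.63. With no effect, no difference is created.
- Wider grid: true effect 4 mmHg, uniform or truncated normal baseline, 50% or 100% of the effect at week 12, correlation 0.5 or 0.8, and 25% to 100% of those at 50 or above or below 30 leaving. Losses are 3.2% to 18.6% of controls and 3.6% to 23.6% of the liraglutide arm. The difference is 3.15 to 3.96 in completers and 3.70 to 4.43 with week-12 values carried forward.
- Power for 5 mmHg is 91.3% with 22 per arm, 88.5% with 20 and 85.1% with 18.

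No such calculation is offered for HbA1c, dose changes or new medication, because the protocol gives nothing to base one on.

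**The case against.** The strongest objection concerns how the eligibility reason is read. Taken literally, it would disqualify every liraglutide participant at the first dose, since current GLP-1 receptor agonist treatment is an exclusion criterion. The authors more plausibly meant a new disqualifying condition, such as cancer, steroid treatment or severe renal failure. This stands against any fully literal reading. It does not settle which criteria are exempt, and an indication for revascularisation fits the natural reading while being tied to limb outcome.

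A reader might infer that the protocol makes success on the co-primary TcPO₂ outcome a trigger for withdrawal. The document does not support that. The 30 to 49 mmHg range sits in the Study population paragraph and not among the inclusion bullets, TcPO₂ is scheduled to be measured at week 24, and the wording permits exit and does not require it. The TcPO₂ arithmetic shows only what the broad reading would entail.

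Both reasons are also in the participants' list, and participants can leave at will anyway. That is fair, but an item such as poor adherence suggests a decision made by the study team, and a protocol that lists these events as reasons to leave gives no ground for asking the participant to stay.

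Finally, control prescriptions are part of the assigned strategy and may be implicitly exempt from the medication reason. The extension rule governs only additional analyses and withdraws nobody from the 24-week trial. It shows that the authors treat a change of glucose-lowering therapy as disqualifying in one setting, and no more. Still, the withdrawal section states no exemption.

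**Conclusion.** The concern holds in a limited form. The withdrawal section does not distinguish stopping treatment from leaving the study. It permits exit, in either arm, for events that can be related to outcome or to the control arm's assigned care. The conclusion does not depend on TcPO₂: HbA1c, stable background doses, revascularisation and new medication are enough. If the reasons are used, the week-24 values are missing informatively and cannot be recovered in analysis.

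The rate, direction and size of any bias cannot be derived from the document. The simulations rest on assumed exit fractions and on the broad TcPO₂ reading. They suggest a modest distortion that can go either way depending on how missing values are handled, and none when there is no treatment effect and the TcPO₂ reason is applied alike in both arms. A reader might infer that the trial's result is biased, or that the protocol contradicts itself; neither follows. This is a rule that should be tightened, and a cheap improvement.

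**What to change.** Add to Study withdrawal that, in both arms, new medication (including therapy prescribed under Interventions) or a change in eligibility status after randomisation may lead to study drug being stopped for safety but does not end follow-up. Such participants attend the planned week-12 and week-24 visits, have the new drug and its start date recorded, and are analysed as randomised. The right to withdraw by choice is unchanged. Add a sensitivity analysis for participants who started a new glucose-lowering drug; its details can sit in a statistical analysis plan.

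The cost is one or two sentences and one extra item recorded at visits already scheduled, with no new assays. The downside is that participants whose background therapy has changed stay in the primary comparison and may dilute the contrast. That could include controls given a GLP-1 receptor agonist, which the control-arm text does not bar. The sensitivity analysis would show how much this matters.
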